2.8.2 Vital signs

Vital signs measurements include systolic and diastolic blood pressure (SBP and DBP), pulse rate, temperature, height and body weight. Vital signs data taken on or after the time of the first intake of study treatment and until the day after the last intake of study drug are regarded as on-treatment data. Vital signs data measured more than 1 day after last intake of study drug are

regarded as post-treatment data and will not be summarized. All data will be included in the analyses regardless of rescue medication use.

The following analyses will be performed by treatment group:

- the number and percentage of patients with newly occurring or worsening notable vital signs on-treatment values (see [Table 2.8.2](#) for definition of notable values) summarized by parameter (except height), at any time on treatment considering all post-baseline data from scheduled, unscheduled and premature discontinuation visits
- Vital signs will also be summarized by clinically relevant categories at the baseline and the week 16 visits :
 1. Pulse rate: < 40 bpm, 40 – 90 bpm, and > 90 bpm
 2. Systolic blood pressure: < 90 mm Hg, 90 – 140 mm Hg, and > 140 mm Hg
 3. Diastolic blood pressure: < 50 mm Hg, 50 – 90 mm Hg, and > 90 mm Hg.

The same approach as for notable laboratory values will be used to define a newly occurring notable vital sign value and a worsening notable vital sign value.

A listing of all patients with notable vital sign values and changes will be provided.

Table 2.8.2 Clinical notable criteria for vital signs

Vital sign parameter (unit)	Lower bound of clinically notable range	Upper bound of clinically notable range
Notable values		
Systolic blood pressure (mmHg)	< 75	> 200
Diastolic blood pressure (mmHg)	< 40	> 115
Pulse rate (bpm)	< 40	> 130
Notable change from baseline		
Systolic blood pressure (mmHg)	≤ 90 and decrease from baseline by ≥ 20	≥ 180 and increase from baseline by ≥ 20
Diastolic blood pressure (mmHg)	≤ 50 and decrease from baseline by ≥ 15	≥ 105 and increase from baseline by ≥ 15
Pulse rate (bpm)	≤ 50 and decrease from baseline by ≥ 15	≥ 120 and increase from baseline by ≥ 15
Weight (kg)	Decrease ≥ 7% from baseline	Increase ≥ 7% from baseline

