- QAW039 has been well tolerated in populations studied to date at total daily doses up to 500 mg given for up to 12 weeks. In the 10 completed studies, 16 patients reported 17 SAEs, no deaths due to SAEs were reported, and 5 discontinuations due to SAEs were reported. Of the 16 patients reporting SAEs, 12 patients reported 13 events, 2 patients reported 2 events and 2 patients reported 2 events in the QAW039, placebo, and montelukast treatment groups, respectively. There were no SAEs with a suspected causal relationship to QAW039. There have been no adverse events of idiopathic drug reactions.
- Cardiovascular risks: Transient, increases in heart rate were observed in a cardiovascular safety pharmacology study in dogs. These changes were not associated with any significant alterations in blood pressure, ECG interval duration, morphology or rhythm or any structural changes in cardiac tissues. No cardiac findings have been identified in the healthy volunteer and patient studies completed to date apart from an observed imbalance in the frequency of post-randomization cardiac adverse events in study [CQAW039A2206] with a higher incidence in the QAW039 treatment group (1.7%) compared with either placebo (0.7%) or montelukast (0%) treated patients. The cardiac events comprised a number of different non-serious arrhythmias and one serious adverse event of pericarditis not suspected to be related to study drug by the Investigator. Three of the events in the QAW039 treatment groups occurred during the washout period and

resolved on treatment. Based on the inability to identify discernable trends with QAW039 dose, regimen, time-of-onset, patient age and gender, concomitant medication, event type and following detail ECG review, it was considered that these were most probably coincidental events without a causal association to study drug. A formal QTc study has not been completed for QAW039. Monitoring for changes in vital signs, ECGs and biochemical parameters will be conducted.

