**Table 8-1 Assessment Schedule**

Period	Screening			Treatment					
Visit Name	Screening	Run-in 		Treatment				EOT or TD	Follow-up
Days	-42 to -28	-28 to -1	1	1	28	56	84	112	124
Weeks	-6 to -4	-4 to -1	1	1	4	8	12	16	18
Informed consent	X								
Inclusion / Exclusion criteria	X	X	X						
Demography	X								
Physical Examination	S							S	
Medical history/current medical conditions	X								
Surgeries and Procedures	X								
Prior medications	X								
Safety Follow up Call									S
ACQ-5	X								
Vital Signs	X	X	X		X	X	X	X	
Body Height	X								
Electrocardiogram (ECG)	X		X					X	
Body Weight	X								
Pregnancy Test (serum)	X								
Pregnancy Test (Urine)			S		S	S	S	S	
Hematology	X		X			X		X	
HbA1C	X							X	
Clinical Chemistry	X		X			X		X	
Urinalysis	X		X						
Check IMP Compliance					S	S	S	S	
Contact IRT (IVRS/IWRS)	S	S	S	S	S	S	S	S	
Randomization				S					

Period	Screening			Treatment					
Visit Name	Screening	Run-in 		Treatment				EOT or TD	Follow-up
Days	-42 to -28	-28 to -1	1	1	28	56	84	112	124
Weeks	-6 to -4	-4 to -1	1	1	4	8	12	16	18
Study Drug Dispensation				S	S	S	S		
Study drug administration				Daily					
SoC/Rescue Medication Dispense		S	S	S	S	S	S		
Adverse Events	X	X	X		X	X	X	X	X
Serious Adverse Events	X	X	X		X	X	X	X	X
Concomitant medications	X	X	X		X	X	X	X	X
Liver Event Monitoring 	X	X	X	X	X	X	X	X	X
Renal Event Monitoring 	X	X	X	X	X	X	X	X	X
Nasal Endoscopy 	X		X			X		X	
Nasal Congestion Score Questionnaire	X	X	X		X	X	X	X	
QoL Questionnaire (SNOT-22)	X	X	X		X	X	X	X	
Smell Assessment (UPSIT)	X	X	X		X	X	X	X	
Study completion information								X	

X Assessment to be recorded in the clinical database or received electronically from a vendor

S Assessment to be recorded in the source documentation only

 Assessments at Run-in Day 1 will be performed prior to Randomization. Run-in Day 1 and the Treatment Day 1 visit will take place on the same day if the patient is randomized

 Please refer to protocol [Section 10.2.1](#)

 Please refer to protocol [Section 10.2.2](#)

 Nasal polyp score will be determined by central reading.

 [REDACTED]

 For patient familiarization with device only.

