**Table 8-3 Physical Assessments**

Assessment	Specification
Physical examination	
A complete physical examination will include the examination of general appearance, skin, neck (including thyroid), eyes, ears, nose, throat, lungs, heart, abdomen, back, lymph nodes, extremities, vascular, and neurological. If indicated based on medical history and/or symptoms, rectal, external genitalia, breast, and pelvic exams will be performed.
 
Information for all physical examinations must be included in the source documentation at the study site. Clinically relevant findings that are present prior to signing informed consent must be recorded on the appropriate CRF that captures medical history. Significant findings made after first administration of investigational drug which meet the definition of an Adverse Event must be recorded as an adverse event.

Assessment	Specification
Vital signs	Vital signs include blood pressure and pulse measurements. After the subject has been sitting for five minutes, with back supported and both feet placed on the floor, systolic and diastolic blood pressure will be measured three times using an automated validated device, e.g. OMRON, with an appropriately sized cuff. The repeat sitting measurements will be made at 1 - 2 minute intervals and the mean of the three measurements will be used. In case the cuff sizes available are not large enough for the subject's arm circumference, a sphygmomanometer with an appropriately sized cuff may be used.
Height and weight	Height in centimeters (cm) and body weight (to the nearest 0.1 kilogram (kg) in indoor clothing, but without shoes) will be measured.

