### **Vital signs**

All vital signs data will be listed by treatment group, On-treatment notable vital signs abnormalities will be summarized by treatment group.

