2.7.7.1 Summary of change from baseline

For continuous laboratory parameters, the on-treatment change from baseline to the worst post-baseline values (including values from post-baseline unscheduled and premature discontinuation visits) will be summarized by laboratory parameter and treatment group with standard descriptive statistics.

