2.8 Other safety data

2.8.1 ECG and cardiac imaging data

ECG measurements include heart rate, QT interval, RR interval, PR interval, QRS duration, and Fridericia's QTc (calculated as $QTcF = QT / \sqrt[3]{RR}$ (in seconds), where $\sqrt[3]{}$ denotes the cube root).

ECG data measured more than 1 day after last intake of study drug are regarded as post treatment data and will not be summarized. All data will be included in the analyses regardless of rescue medication use.

Clinically relevant values

- The number and percentage of patients with newly occurring or worsening clinical relevant QTcF values (see [Table 2.8.1](#)) summarized at any time on treatment considering all post-baseline data from scheduled, unscheduled and premature discontinuation visits.

Table 2.8.1 Clinically relevant criteria for QTcF (Fridericia's formula)

ECG parameter (unit)	Clinically relevant range
Value considering newly occurring or worsening cases	
QTcF (msec)	≥ 450 (male)
QTcF (msec)	≥ 460 (female)
QTcF (msec)	> 500 (both)
Change from baseline	
QTcF	< 30
QTcF	30 – 60
QTcF	> 60

Clinically notable values

- A summary table will also be produced for number and percentage of subjects with notable QT and QTcF intervals (irrespective of the time point) using the following categories:
 - any treatment emergent (new) QTcF or QT interval ≥ 450 ms – 480 ms, > 480 ms – 500 ms or > 500 ms
 - QTcF or QT increase from baseline of ≥ 30 ms – < 60 ms, ≥ 60 ms
 - QTcF and QT increase from baseline of ≥ 30 ms plus QTcF interval ≥ 450 ms, > 480 ms or > 500 ms
 - QTcF increase from baseline of ≥ 60 ms plus QTcF interval ≥ 450 ms, > 480 ms or > 500 ms
- The number and percentage of subjects with noteworthy PR, QRS and HR interval changes will be reported using the below categories:
 - New PR > 200 ms to ≤ 220 ms; and > 220 ms
 - New QRS > 110 ms to ≤ 120 ms; and > 120 ms
 - PR increase $> 25\%$ to a value > 200 ms
 - QRS increase $> 25\%$ to a value > 120 ms
 - HR decrease $> 25\%$ to a HR < 50 bpm
 - HR increase $> 25\%$ to a HR > 100 bpm

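### Pulse, ECG heart rate and QTcF are summarised only by cut-offs and categories, so a modest rise, or one gone by Week 16, could be missed in the summary tables

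*SAP*

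**What the plan says.** **The risk.** Under cardiovascular risks, Protocol 4.5 states: "Transient, increases in heart rate were observed in a cardiovascular safety pharmacology study in dogs". It also reports more cardiac adverse events on fevipiprant (1.7%) than on placebo (0.7%) or montelukast (0%) in an earlier study, and says that no formal QTc study has been completed. It then commits: "Monitoring for changes in vital signs, ECGs and biochemical parameters will be conducted".

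**The data.** Protocol Table 8-3: "Vital signs include blood pressure and pulse measurements". Table 8-1 schedules vital signs before dosing and at Weeks 4, 8, 12 and 16. The only scheduled on-treatment ECG is at Week 16.

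**Pulse analysis (SAP 2.8.2).** Two summaries are planned:
- a count of patients with new or worsening notable values at any time on treatment. On the high side this means above 130 bpm, or at least 120 bpm with a rise of at least 15;
- a table with three pulse categories (below 40, 40 to 90, above 90 bpm): "Vital signs will also be summarized by clinically relevant categories at the baseline and the week 16 visits".

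**ECG analysis (SAP 2.8.1).** "The number and percentage of subjects with noteworthy PR, QRS and HR interval changes will be reported using the below categories". The high-side heart-rate category is a rise of more than 25% to above 100 bpm. QTcF is reported by ranges of value and of change.

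**Contrast with laboratory data (SAP 2.7.7.1).** Continuous laboratory parameters get descriptive statistics for "the on-treatment change from baseline to the worst post-baseline values", and SAP 2.7.7.2 adds box plots of change over time for selected tests.

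**The concern.** The protocol ties a cardiovascular risk to pulse and ECG, and it collects pulse four times on treatment. The SAP then reduces these measurements to threshold crossings. Neither SAP 2.8.1 nor SAP 2.8.2 specifies a mean, or a mean change from baseline, for pulse, ECG heart rate or QTcF, although laboratory data get a change-from-baseline summary.

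Pulse at Weeks 4, 8 and 12 is used only to see whether anyone crossed a notable limit. A rise below those limits that has gone by Week 16 would enter no pulse summary table. A modest sustained rise would move few patients across any limit. The study report could then describe the vital-sign and ECG tables as unremarkable when they had little ability to show a modest shift.

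**Working it through.** **Group size (the plan's own figure).** With difference 1.5, SD 1.8, one-sided alpha 0.0125 and 80% power: n = 2 × [1.8 × (2.2414 + 0.8416) / 1.5]² = 27.4 per arm. Dividing by 0.9 gives 30.4, so 31 per arm and 93 in total, as stated. After 10% dropout, 31 × 0.9 = 27.9, about 28 per arm. The documents give no figure for pulse, heart rate or QTcF, so everything below rests on assumptions.

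**Which visits reach which summary table**

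| Measure | Weeks 4, 8, 12 | Week 16 |
|---|---|---|
| Pulse | notable-value count only | notable-value count; three-category table |
| ECG heart rate | no scheduled ECG | threshold count |
| QTcF | no scheduled ECG | range categories |

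**Assumptions for pulse.** Baseline mean 70 to 75 bpm, between-patient SD 8 to 10, within-patient SD 6 to 7. The SD at one visit is then √(8² + 6²) = 10 to √(10² + 7²) = 12.2. The SD of change is √2 × 6 = 8.5 to √2 × 7 = 9.9. The rise δ is the same in every patient and at all four visits. ECG heart rate is assumed to behave like pulse.

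**Formulas**
- Patients above 90 bpm at Week 16: 28 × [1 − Φ((90 − mean − δ) / SD)]. With mean 70 and SD 10, this is 28 × 0.0228 = 0.6 for δ = 0 and 28 × 0.1151 = 3.2 for δ = 8.
- Notable-pulse and ECG heart-rate counts: by simulation, with the high-side SAP criteria applied to each simulated patient.
- 95% interval for the difference in mean change at one visit: ± 2.005 × SD of change × √(2/28), which is ± 4.5 to 5.3 bpm.
- Power for that difference: two-sample t-test, one-sided 0.025.

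**Expected patients per arm of 28 (range over the assumptions), and power for the mean change**

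| True rise | Notable pulse, any visit | ECG heart-rate criterion | Above 90 bpm, Week 16 | Power, mean change at Week 16 |
|---|---|---|---|---|
| 0 | up to 0.006 | up to 0.06 | 0.6–3.1 | – |
| 5 bpm | up to 0.04 | 0.04–0.3 | 1.9–5.8 | 46–58% |
| 8 bpm | 0.001–0.09 | 0.1–0.6 | 3.2–7.9 | 84–93% |
| 10 bpm | 0.003–0.17 | 0.2–1.0 | 4.4–9.6 | 96–99% |

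As a yardstick only, a Fisher test on the above-90 category would have about 0–8% power at 5 bpm, 5–28% at 8 bpm and 15–53% at 10 bpm.

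**A rise confined to Weeks 4 to 12.** The Week 16 columns return to the first row of the table. Only the notable-pulse column can respond, and with three affected visits instead of four its entries are no larger than those shown.

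**QTcF.** Assume an SD of change of 15 ms. The proportion with a change of at least 30 ms is 1 − Φ((30 − δ) / 15): 2.3% for no shift, 4.8% for 5 ms and 9.1% for 10 ms. In 28 patients that is 0.6, 1.3 and 2.6. The interval for the mean difference is ± 2.005 × 15 × √(2/28) = ± 8.0 ms, and power for the mean change is about 23% at 5 ms and 69% at 10 ms. The interval width scales in proportion to the assumed SD.

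**The case against.** **A reader might infer that a real rise would go unreported, or that the tables could not show one.** The documents do not support either. All vital-sign values are listed by treatment group (Protocol 12.5.1), all safety data are listed (SAP 2.1.3.9), and treatment-emergent adverse events are tabulated by preferred term. The limit of 90 bpm is not extreme: with mean 70 and SD 10, a sustained 8 bpm rise moves the expected Week 16 count from 0.6 to 3.2, which a reader of a descriptive table could notice. What remains is that a listing gives no comparison between arms, and the category table covers only baseline and Week 16.

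**A reader might infer that the SAP falls short of the protocol.** It does not. Protocol 12.5.1 asks for listings and "On-treatment notable vital signs abnormalities will be summarized by treatment group", and for notable ECG abnormalities. The monitoring commitment in Protocol 4.5 is not an analysis specification.

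**The signal is weak.** The heart-rate finding is from dogs, without significant change in blood pressure, ECG intervals or rhythm. Protocol 4.5 reports no human cardiac findings apart from the adverse-event imbalance, which it judges most probably coincidental. It gives no time course for the transient increase, so a rise at Weeks 4 to 12 is a possibility and not a prediction. This stands, and it limits the weight of the point.

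**Power is not a planned criterion.** No test on vital signs or ECG is planned. The power figures only show how much information each summary keeps. At 5 bpm the continuous summary is itself limited.

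**The generic rules may cover it.** SAP 2.1.2 names mean, SD and median for quantitative data, and SAP 2.1.3.8 defines change from baseline by visit. Neither names pulse or ECG, and SAP 2.8.1 and 2.8.2 give their own lists. The rules make the addition routine; they do not make it.

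**Timing.** Clinic doses follow the pre-dose assessments (Protocol 6.7.2). Table 8-1 does not say whether pulse is one of them. If it is, visit means would also miss a brief rise after dosing.

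**Conclusion.** The point holds as a gap in the choice of summaries, not as a conflict between the documents. No change from baseline in pulse, ECG heart rate or QTcF is specified on the continuous scale, and pulse at Weeks 4, 8 and 12 enters only the notable-value count. A modest rise, or one gone by Week 16, could be missed in the summary tables.

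Under the stated assumptions, the notable-pulse count would very probably have no high-side case in an arm even with a 5 bpm rise (at most about 0.04 expected). At 10 bpm it expects at most about 0.17. A rise of 8 to 10 bpm persisting at Week 16 could be visible above 90 bpm. The by-visit mean change would estimate the difference to within about ± 5 bpm. It would be sensitive to 8 to 10 bpm, but has only about 46–58% power for 5 bpm at Week 16. All pulse and QTcF means, SDs and shifts are assumptions. The contrast between cut-offs and means holds across the range shown; the exact counts do not carry over to other values.

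**What to change.** - **SAP 2.8.2:** add a descriptive summary, by treatment group, of change from baseline in pulse, systolic and diastolic blood pressure at Weeks 4, 8, 12 and 16 and to the maximum on-treatment value. Give the difference of each dose from placebo with a 95% confidence interval.
- **SAP 2.8.1:** add the same for ECG heart rate and QTcF at Week 16.
- Label these summaries descriptive and unadjusted for multiplicity, and keep the existing notable-value tables.
- If a detectable effect is quoted in support, show it over a range (for example 5, 8 and 10 bpm), because no document gives a value.

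**Cost.** SAP wording and a few tables from data already collected, with no new visits, procedures or patients. The downside is more unadjusted intervals: 3 vital signs × 5 summaries × 2 doses = 30, plus 2 ECG measures × 2 doses = 4, so 34 in all. With no true effect, about 34 × 0.05 = 1.7 would exclude zero by chance, which is why the descriptive label matters.

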2.9 Pharmacokinetic endpoints

Not Applicable

2.10 PD and PK/PD analyses

[figure not shown]
Not Applicable.

2.11 Patient-reported outcomes

Nasal Congestion Score, SNOT 22 and UPSIT are the Patient reported outcomes questionnaires that we would be collecting in this study. Endpoints related to these questionnaires and analysis method described in section 2.7.1.

2.12 Biomarkers

Not Applicable

2.14 Interim analysis

No interim analysis is planned.

3 Sample size calculation

Based on clinical judgement a mean reduction of 1.5 in polyp score (as measured by the NPS) can be expected with fevipiprant (450 mg and 150 mg) and SoC as compared to Placebo and SoC. Considering this factor, the sample size was calculated under an 80% power and 1.25% one sided alpha for comparison of each of the two dose levels of fevipiprant and SoC with placebo and SoC. A 10% dropout rate is considered as appropriate with reference to prior studies (omalizumab study by Gevaert et al 2013 and dupilumab study by Bachert et al 2016). From prior literature standard deviation of 1.8 is considered as appropriate for the change of score from baseline at 16 weeks in Nasal Polyp Score.

The sample size calculation was performed using the software PASS 2008 using inequality tests using difference of two independent means with equal variance.

The randomization will be performed in a 1:1:1 ratio for the two separate doses level of fevipiprant (450 mg and 150 mg) and the placebo arm. Under these assumptions (effect size = 1.5, equal SD = 1.8, power = 80% for each arm individually, one-sided alpha = 0.0125 and dropout = 10%), the total sample size yielded was 93 with 31 patients in each arm. The sample size provides a power of 80% for each comparison but since we will be testing correlated hypothesis using a Dunnett's test, this is a lower bound on the power. The real power is expected to be higher if in at least one of the 2 dosages i.e. fevipiprant 150 mg or fevipiprant 450 mg, the standardized effect size (in other words, keeping the assumption of an SD of 1.8 in each group) is equal to the clinically significant value of 1.5 and there is some treatment benefit in the other groups as well. However, if the effect size is equal to 1.5 in both of the groups, the power will be substantially higher i.e. around 93%.

4 Change to protocol specified analyses

Not Applicable

5 Appendix

5.1 Imputation rules

5.1.1 AE date imputation

Rules for imputing AE end dates are stated below. Date of last contact in the study has been defined as in Section 2.1.3.11.

1. If the AE end date month is missing, the imputed end date should be set to the earliest of the (date of last contact, 31DECYYYY, date of death).
2. If the AE end date day is missing, the imputed end date should be set to the earliest of the (date of last contact, last day of the month, date of death).
3. If AE year is missing or AE is ongoing, the end date will not be imputed.

5.1.1.1 AE start date imputation

Rules for imputing the AE start date:

The following table explains the notation used in the logic matrix. Please note that **missing start dates** will not be imputed.

	Day	Month	Year
Partial Adverse Event Start Date	Not Used	MON	YYYY
Treatment Start Date	Not Used	TRTM	TRTY

The following matrix explains the logic behind the imputation.

	MON MISSING	MON < TRTM	MON = TRTM	MON > TRTM
YYYY MISSING	(1) No Convention	(1) No Convention	(1) No Convention	(1) No Convention
YYYY < TRTY	(2.a) Before Treatment Start	(2.b) Before Treatment Start	(2.b) Before Treatment Start	(2.b) Before Treatment Start
YYYY = TRTY	(4.a) Uncertain	(4.b) Before Treatment Start	(4.c) Uncertain	(4.c) After Treatment Start
YYYY > TRTY	(3.a) After Treatment Start	(3.b) After Treatment Start	(3.b) After Treatment Start	(3.b) After Treatment Start

Before imputing AE start date, find the AE start reference date.

1. If the imputed AE end date is complete and the imputed AE end date < treatment start date then AE start reference date = min(informed consent date, earliest visit date).
2. Else AE start reference date = treatment start date

Impute AE start date -

1. If the AE start date year value is missing, the date uncertainty is too high to impute a rational date. Therefore, if the AE year value is missing, the imputed AE start date is set to NULL.
2. If the AE start date year value is less than the treatment start date year value, the AE started before treatment. Therefore:
 - a. If AE month is missing, the imputed AE start date is set to the mid-year point (01JulYYYY).
 - b. Else if AE month is not missing, the imputed AE start date is set to the mid-month point (15MONYYYY).
3. If the AE start date year value is greater than the treatment start date year value, the AE started after treatment. Therefore:
 - a. If the AE month is missing, the imputed AE start date is set to the year start point (01JanYYYY).
 - b. Else if the AE month is not missing, the imputed AE start date is set to the later of (month start point (01MONYYYY), AE start reference date + 1 day).
4. If the AE start date year value is equal to the treatment start date year value:
 - a. And the AE month is missing the imputed AE start date is set to the AE reference start date + 1 day.
 - b. Else if the AE month is less than the treatment start month, the imputed AE start date is set to the mid-month point (15MONYYYY).
 - c. Else if the AE month is equal to the treatment start date month or greater than the treatment start date month, the imputed AE start date is set to the later of (month start point (01MONYYYY), AE start reference date + 1 day).

If complete imputed AE end date is available and the imputed AE start date is greater than the imputed AE end date, then imputed AE start date should be set to the imputed AE end date.

